# 11.5 Sample Size

It is anticipated that this study will last approximately 42 months (30 months of accrual and 12 months of additional follow-up while cohort matures). The total enrollment will be 38. With a 1 to 5 ratio of prior RT treatment to no prior RT treatment, we expect to enroll approximately 6 subjects in Cohort A and 30 in Cohort B. Six subjects in Cohort A will allow us to obtain only a preliminary sense of efficacy; however, we do not want to exclude this important cohort from the study since our focus is on safety. A sample size of 38 will allow us to estimate the primary outcome of acute (within 3 months of treatment) grade 3 or greater gastrointestinal and hematologic toxicity to within approximately 12% using a 90% exact confidence interval assuming the rate is similar to Herman et al. (28%).

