#### 11.2 Study Design

This is an open-label pilot study. No randomization or blinding is involved. Patients will be placed into dosing cohorts (A or B) depending on previous radiation therapy and followed for at least 1 year post-SBRT.

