# 11.3 Criteria for Stopping Study

We expect the safety profile to be similar for Cohort A and B so will evaluate the stopping rule in the combined cohort. The expected Grade 4 or 5 treatment related AE rate from gemcitabine with SBRT is approximately 6% (Herman ref), and we would consider a 10% rate in our study to be unacceptable. An interim safety analysis is planned after every six patients are accrued and followed for 1 year to assess Grade 4 or 5 treatment-related AEs. If 3 or more out of 6, 4 or more out of 12, 5 or more out of 18, or 6 or more out of 24 patients have a Grade 4 or 5 treatment-related AE within one year, accrual will be terminated. These stopping boundaries represent where the lower bound of a 90% exact binomial confidence interval would be in excess of 10%.

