#### 11.9 Analysis of Primary Objective

The primary outcome of acute (within 3 months of treatment) grade 3 or greater gastrointestinal and hematologic toxicity will be estimated with a 90% exact binomial

Protocol Version Date: 07/02/2024 Page 21

confidence interval in the two cohorts combined, since the safety profile is expected to be similar for Cohort A and B.

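### The 12-point precision claimed for the primary toxicity rate is not what a 90% exact interval gives with 38 patients (about 12 points below, 14 above), and the expected cohort sizes add to 36

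*Combined protocol and SAP*

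**What the plan says.** Section 11.5 (Sample Size) fixes the sample size: "The total enrollment will be 38". It states that this number will estimate the primary outcome, acute grade 3 or greater gastrointestinal and hematologic toxicity within 3 months, "to within approximately 12% using a 90% exact confidence interval", at an assumed rate of 28% taken from a cited earlier trial.

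Section 11.9 (Analysis of Primary Objective) plans the same kind of interval for the analysis, with both cohorts pooled: the outcome "will be estimated with a 90% exact binomial" confidence interval.

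On the make-up of the sample, section 11.5 assumes one patient with prior radiotherapy for every five without, and continues: "we expect to enroll approximately 6 subjects in Cohort A and 30 in Cohort B".

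Two other sections bear on the point. Section 11.2 says "This is an open-label pilot study". Section 11.3 uses the same type of interval for the stopping boundaries on grade 4 or 5 treatment-related events, which it describes as the points where "the lower bound of a 90% exact binomial confidence interval would be in excess of 10" percent.

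**The concern.** A single figure of 12 points suggests that the interval reaches about 12 points either side of the estimate. An exact binomial interval around a rate near 28% is not symmetric: it reaches further upward than downward. It is also usually somewhat wider than the normal approximation. A symmetric 12 points with 38 patients therefore looks as if it came from a different method from the one named.

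The study has no hypothesis test and no target for the primary rate, so this sentence is the whole quantitative case for 38 patients. The side that is understated is the upper one, which tells the reader how high a toxicity rate the data could still be compatible with.

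The cohort sizes are a separate, smaller matter. The two expected counts should add to the total given in the same paragraph, and they do not.

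**Working it through.** **Inputs.** All are from section 11.5: n = 38, assumed rate 28%, 90% two-sided exact interval (5% in each tail), expected cohorts 6 and 30, ratio 1:5. The expected count is 0.28 × 38 = 10.64, so the nearest results that can be observed are 10/38 (26.3%) and 11/38 (28.9%).

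**Reproducing the plan's figure.** The normal-approximation half-width is 1.645 × √(p(1−p)/n).

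- n = 38: 1.645 × √(0.28 × 0.72/38) = 11.98 points.
- n = 37: 12.14 points.
- Solving for exactly 12 points: n = 1.645² × 0.28 × 0.72/0.12² = 37.88.

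So 38 is the smallest n that gives 12 points or less by this formula. The match suggests where the figure came from but does not prove it.

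**The interval the plan names.** The Clopper-Pearson limits for x events in n are

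- lower = the 5th percentile of Beta(x, n − x + 1),
- upper = the 95th percentile of Beta(x + 1, n − x).

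| Result, n = 38 | 90% interval | Below estimate | Above estimate | Half-width |
|---|---|---|---|---|
| 10 events (26.3%) | 15.0% to 40.5% | 11.3 | 14.2 | 12.75 |
| 11 events (28.9%) | 17.2% to 43.3% | 11.8 | 14.4 | 13.09 |
| 28% exactly (10.64 events put into the same formula) | 16.4% to 42.3% | 11.6 | 14.3 | 12.97 |

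The lower arm is within 12 points. The upper arm is about 2 points over (14.2 − 12 = 2.2; 14.4 − 12 = 2.4), and the half-width is about 1 point over.

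**Sample size that 12 points would need.** At a rate of 28%, the Clopper-Pearson half-width first falls to 12 points or less at n = 45 (it is 12.01 at n = 44). The upper arm does so at n = 52. These figures only show the size of the gap; they are not a proposal to enlarge the study.

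**Other readings of exact.** The plan does not name Clopper-Pearson, so two alternatives were tried.

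| Method, n = 38 | Events | 90% interval | Below | Above | Half-width |
|---|---|---|---|---|---|
| Mid-P | 10 | 15.9% to 39.3% | 10.4 | 13.0 | 11.7 |
| Mid-P | 11 | 18.1% to 42.1% | 10.9 | 13.2 | 12.0 |
| Blaker | 10 | 15.3% to 39.5% | 11.0 | 13.2 | 12.1 |
| Blaker | 11 | 18.1% to 43.3% | 10.9 | 14.4 | 12.6 |

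Across all three methods the upper arm runs from 13.0 to 14.4 points.

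**Consistency with the plan's other exact interval.** Clopper-Pearson lower bounds at the stopping boundaries in section 11.3 are 15.3% (3/6), 12.3% (4/12), 11.6% (5/18) and 11.5% (6/24). With one event fewer they are 6.3%, 7.2%, 8.0% and 8.6%. All four stated boundaries are therefore reproduced. Mid-P reproduces the same four, so this supports the Clopper-Pearson reading without settling it.

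**Cohort sizes.** 6 + 30 = 36, and 38 − 36 = 2. A 1:5 ratio gives exactly 6 and 30 when the total is 36. With 38 it gives 38/6 = 6.3 and 38 × 5/6 = 31.7, or about 6 and 32. Section 11.5 states no allowance for dropout or unevaluable patients. If the two extra patients were such an allowance and 36 were analysed, the exact interval at 28% would reach 11.9 points below and 14.8 above.

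**The case against.** The arithmetic is not in dispute; the objection is to calling the statement wrong.

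The text says approximately, and a single plus-or-minus figure is normally read as a half-width. On that reading the gap is only 0.75 to 1.1 points. The plan never says which exact interval it means: with mid-P the half-width is 12.0 at 11/38, and with Blaker's interval it is 12.1 at 10/38. The normal approximation as the source of the figure is an inference. Nothing in the plan turns on the number: the study is a pilot, the interval will be computed from the observed data, no threshold is set for the primary rate, and the only stopping rule uses another endpoint and a lower bound. The cohort sizes are forecasts of a split that depends on who has had prior radiotherapy; they are not quotas. The primary analysis pools the cohorts in any case.

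Most of this stands as a limit on the importance of the point. It does not rescue the figure as written. Under the usual meaning of an exact binomial interval the half-width is nearer 13 than 12, and the upper arm exceeds 12 under each of the three methods tried. The source of the figure does not affect that conclusion. On the cohorts, the word approximately softens the mismatch, but the 1:5 ratio and the two counts fit 36 exactly, so the paragraph appears to use two different totals.

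**Conclusion.** The point holds and is small. With 38 patients and a rate near 28%, the 90% exact interval reaches about 12 points below the estimate and about 14 above. The stated precision is met on the lower side and exceeded by about 2 points on the upper side. An observed rate of 28% would leave rates up to about 42% inside the interval, where a reader of section 11.5 would expect 28 + 12 = 40%. Separately, the expected cohort sizes fall two short of the stated total, with no explanation.

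This rests on reading exact as Clopper-Pearson and on the 28% given in section 11.5, whose source was not checked. With mid-P or Blaker limits the excess on the upper side is 1.0 to 2.4 points. Neither the sample size nor any analysis or decision rule is put in doubt. The correction should still be made, because this sentence is the only numerical justification for the sample size.

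**What to change.** Keep 38 patients and restate the precision in section 11.5, for example: With 38 patients and 11 events (28.9%), the 90% exact (Clopper-Pearson) interval is 17% to 43%, about 12 points below and 14 points above the estimate. Name the same interval method in section 11.9.

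Reconcile the cohort counts with the total. Either give the expected sizes as about 6 and 32, which is a 1:5 split of 38, or say what the two additional patients are for. If they are an allowance for unevaluable patients, state the precision for 36.

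The cost is one or two sentences in section 11.5 and a few words in section 11.9. The precision will read slightly less favourably. Sample size, analysis and stopping rule stay as they are.

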#### 11.6 Patient Characteristics and Significant Protocol Violations

Baseline patient characteristics will be tabulated, such as demographics (age, race, gender), and disease characteristics will be displayed combined and by cohort. Significant protocol violations such as with respect to eligibility criteria and treatment plan will be tabulated by cohort.

#### 11.7 Concomitant Medications

Medications that might affect the study treatment will be tabulated.

## 11.8 Disposition

Frequencies and percentages of all patients enrolled, discontinuing the study, and completing the study will be presented by cohort. The reasons for discontinuation will also be summarized.

#### 11.9 Analysis of Primary Objective

The primary outcome of acute (within 3 months of treatment) grade 3 or greater gastrointestinal and hematologic toxicity will be estimated with a 90% exact binomial

Protocol Version Date: 07/02/2024 Page 21

confidence interval in the two cohorts combined, since the safety profile is expected to be similar for Cohort A and B.

# 11.10 Analysis of Secondary Objectives

Acute toxicities according to CTCAE 4.0 will be summarized by frequencies and rates calculated as the proportion of patients in the safety population experiencing SAEs, discontinuations due to AEs, and AEs for the two cohorts combined. For the secondary objective of estimating rates of late (> 3 months after treatment) grade 2 gastritis, enteritis, fistula, and ulcer, or any other grade 3 or greater gastrointestinal toxicity, the proportion of patients with each condition and its 90% confidence interval will be calculated.

In Cohort B only, Kaplan-Meier estimates will be used to estimate the median and 90% confidence intervals for time to local progression, overall survival, metastasis-free survival and progression-free survival. The 1-year rates and 90% confidence intervals will be also be estimated from these curves. A listing of clinical outcomes will be generated for Cohort A.

Pain control (based on reporting of standard pain score (0-10) with the option to use the FACES 0-10 scale) will be evaluated before and after Linac-based SBRT and the change in pain scores will be evaluated and summarized through descriptive statistics separately for each cohort. For Cohort B, linear mixed models will be used to model changes in pain over time. A similar approach will be used for the EORTC QOL-Q scale.

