# 2.2 Rationale for the use of stereotactic body radiation therapy in pancreatic cancer

Recent advances in radiation treatment technology, including improvements in planning systems, patient immobilization equipment, image-guided radiation therapy technologies, and radiation delivery mechanisms, have permitted the development of stereotactic body radiation therapy (SBRT), which permits the intensification of therapy by delivering increased daily doses of radiation to highly focused targets within the body. Several phase II trials of SBRT in patients with pancreatic cancers have been performed, showing that the technique is well tolerated and is associated with improvements in local control rates compared with historical series of conventionally fractionated chemoradiation. Koong et al. used the Cyberknife™ stereotactic radiosurgery system to demonstrate that a single 25-Gy dose stereotactic body radiotherapy (SBRT) was feasible for patients with locally advanced pancreatic cancer. (17) Furthermore, this dose of radiation resulted in near 100% progression free survival and effectively palliated symptoms related to the local growth of pancreatic tumors. Based on this study, the same group also completed a phase II study assessing the efficacy of combining a standard fiveweek course of chemoradiotherapy followed by a stereotactic radiosurgery boost to the primary tumor in patients with locally advanced pancreatic cancer. In this cohort of 19 patients, 100% of tumors were without local progression. However, all patients eventually developed metastases, with a median time to progression of 5.5 weeks. A more recent phase II study treated locally advanced pancreatic cancer patients with induction gemcitabine followed by single-fraction SBRT (25 Gy) and maintenance gemcitabine chemotherapy. In this study, the excellent progression free survival was confirmed from previous studies (81%). The median overall survival was 11.4 months, median time to progression was 9.7 months and the 1 year survival was 50%.(18) There were no significant acute GI toxicities; however, of the 15 patients alive >6 months after Linac

(linear-accelerator)-based SBRT, 7 (47%) experienced Grade 2 or greater GI toxicity, with 2 (13%) of the 15 experiencing Grade 3 or greater GI toxicity.

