#### 3.3.2 Secondary Outcome Measures

• Late (> 3 months after treatment) toxicity rates (as raw percentage), as related to the RTOG Late Radiation Toxicity Grading Scale.

- One-year rates of overall, progression-free, and metastasis-free survival (will
  continue to obtain data on these outcomes at subsequent visits beyond 1
  year, but the 1 year time point will represent the outcome measure of
  interest)
- Pain control at one and three months after treatment (based on reporting of standard pain score (0-10) with an option to record pain score based on FACES assessment scale) –will continue to obtain data on pain control at subsequent visits but these 2 time points will represent the main outcome measures of interest
- Quality of life at each follow-up visit (measured by EORTC QOL-Q scale) will
  continue to obtain data on quality of life at subsequent visits but these 2 time
  points will represent the main outcome measures of interest

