# 7.3 Follow-Up

Following Linac-based SBRT, all patients will be monitored clinically and with serial imaging (CT scans and/or PET/CT if possible and as deemed necessary by the treating physician). A detailed medical history with physical examination and quality of life assessment will be performed at 4-6 weeks, 4 months, 6 months, 9 months and 1 year after radiation treatment. In years 2-5, the follow up interval will be every 3-6 months, as determined by the principal investigator. Follow up intervals may also be more frequent as indicated clinically. A complete blood count (CBC) with differential, comprehensive chemistry panel, tumor marker studies, and quality of life assessment will be performed at each follow-up interval.

We estimate that most patients will remain a subject in this study for approximately one year. Patients will remain enrolled on this protocol for a maximum of 5 years or until patient withdrawal. Patients that have completed the 5 year follow-up will continue being followed for survival information until death. The administration of subsequent chemotherapy and/or other antineoplastic treatment following Linac-based SBRT will be at the discretion of each patient's attending medical oncologist. If participants become very ill and cannot travel to IU for follow-up appointments, the study team will mail Quality of Life Questionnaires and request relevant medical records from local providers. This situation is expected due to progression profile, and if all protocol parameters are met, will not constitute a protocol deviation.

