#### 11.4 Analysis Datasets

- Enrolled Population The enrolled population consists of all patients who enroll in the study.
- Efficacy Population The efficacy population comprises all patients who meet
  the eligibility criteria, are registered onto the study, get at least one session of
  Linac-based SBRT, and have at least one follow-up evaluation. This set will be
  used for efficacy analysis.
- Safety Population The safety population comprises all patients who have received at least one session of Linac-based SBRT. This set will be used for safety analysis.

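### Late toxicity is planned as a raw percentage with no time horizon and no handling of death or incomplete follow-up, so it estimates no defined risk

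*Combined protocol and SAP*

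**What the plan says.** Section 3.3.2 lists the outcome as "Late (> 3 months after treatment) toxicity rates (as raw percentage), as related to the RTOG Late Radiation Toxicity Grading Scale". For the late events defined in Section 3.2, Section 11.10 says that "the proportion of patients with each condition and its 90% confidence interval will be calculated". That sentence names no population. Section 11.4 assigns safety analysis to the safety population: "The safety population comprises all patients who have received at least one session of Linac-based SBRT". By default, then, a patient who dies or is lost before month 3 stays in the denominator.

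Neither section says by when a late event must have occurred, or what happens to patients who die or leave follow-up. Time-to-event methods are planned only for efficacy: "In Cohort B only, Kaplan-Meier estimates will be used to estimate the median and 90% confidence intervals for time to local progression" and the survival outcomes. Section 11.1 rules out imputation of missing data.

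On follow-up, Section 11.2 has patients "followed for at least 1 year post-SBRT", and Section 7.3 adds: "Patients will remain enrolled on this protocol for a maximum of 5 years or until patient withdrawal". Section 11.5 plans 30 months of accrual and a further 12 months.

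The protocol offers two reference points. Section 8 expects late gastrointestinal toxicity of grade 2 or more in at most 20% of patients within one year. Section 2.2 gives the late toxicity of the cited single-fraction study as a share "of the 15 patients alive >6 months after Linac"-based SBRT.

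**The concern.** A crude proportion equals the risk by a given time only if that time is fixed and every patient is followed to it or to death. The plan fixes no such time for late toxicity, although it does so for the neighbouring outcomes: three months for acute toxicity, one year for the survival outcomes, and one year for the grade 4 or 5 events in the stopping rule of Section 11.3.

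Late bowel injury is the reason Section 2.2 gives for moving from one fraction to five, and Section 8 treats duodenal and gastric ulceration as the chief serious harm. If the reported percentage depends on when the data are cut and on who was lost, a reader cannot tell whether a difference from the one-year expectation reflects the treatment or the follow-up.

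**Working it through.** **The plan's own figure.** No precision is stated for late toxicity. The only such figure is for the acute primary outcome (Section 11.5: 38 patients, rate 28%, 90% interval, about 12 points). 1.645 × √(0.28 × 0.72 / 38) = 0.120, which agrees. Exact intervals are slightly wider (half-width 12.8 points at 10/38 and 13.1 at 11/38). Nothing below depends on this.

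**Inputs**

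| Input | Value | Source |
|---|---|---|
| Late window opens | month 3 | Sections 3.2 and 3.3.2 |
| Median survival | 13.8 and 11.4 months; 7 months | cited five-fraction and single-fraction studies (2.2); isolated locoregional recurrence (2.3) |
| Potential follow-up at study month 42 | 12 to 42 months | Section 11.5 |
| Late risk, months 3 to 12, in the absence of death | 20% (11% also tried) | assumption, set at the Section 8 expectation; 11% is the late rate quoted in 2.2 for the five-fraction study |
| Lost by month 12 | 20% (10% and 30% also tried) | assumption; the documents give no rate |

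**Model.** Constant hazards. Death: d = ln 2 / median. Late event from month 3: a = −ln(1 − 0.20)/9 = 0.0248 per month.

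- Alive at month 3: S3 = exp(−3d).
- Cumulative incidence by month T among those alive at month 3: C(T) = a/(a + d) × [1 − exp(−(a + d)(T − 3))].
- Cumulative incidence over all treated patients: S3 × C(T).
- Raw proportion at month 12 with loss hazard c = −ln(1 − 0.20)/12 = 0.0186, lost patients counted as event-free: exp(−3(d + c)) × a/(a + d + c) × [1 − exp(−9(a + d + c))].
- Raw proportion with no horizon and no loss: S3 × the average of C(T) for T uniform over 12 to 42.

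Example, median 13.8 months: d = 0.0502, S3 = 0.8601, a/(a + d) = 0.330, 1 − exp(−9 × 0.0750) = 0.491. So C(12) = 0.162, and over all treated patients 0.140.

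| 20% input | Median 7 | Median 11.4 | Median 13.8 |
|---|---|---|---|
| Dead before month 3 (of 38) | 26% (about 10) | 17% (about 6) | 14% (about 5) |
| (1) 12-month cumulative incidence, all treated | 10.0% | 13.0% | 14.0% |
| (2) Same, among patients alive at month 3 | 13.5% | 15.6% | 16.2% |
| (3) Raw at month 12, 20% lost | 8.8% | 11.4% | 12.3% |
| (4) Raw, no horizon, 12 to 42 months, no loss | 13.6% | 20.1% | 22.7% |

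**Reading the rows**

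- (3) against (1): loss lowers the figure by 1.2 to 1.7 points. Across 10% to 30% loss, row (3) runs from 9.4% to 8.2% at median 7 and from 13.1% to 11.4% at median 13.8.
- (4) against (1): events after one year raise the figure by 3.6 to 8.7 points.
- (2) against (1): the all-treated figure is 2.3 to 3.5 points lower, but the two rows answer different questions.

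With the 11% input the pattern is the same: row (1) 5.5%, 7.1%, 7.6%; row (2) 7.3%, 8.5%, 8.9%; row (4) 7.7%, 11.6%, 13.2%.

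**In counts.** Four late events read as 4/38 = 10.5% (90% exact interval 3.7 to 22.5), 4/32 = 12.5% (4.4 to 26.4) or 4/28 = 14.3% (5.0 to 29.8), according to whether 0, 6 or 10 early deaths leave the denominator.

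**The case against.** The other side has substance. The Section 8 expectation is worded for patients, not for survivors to month 3, so an all-treated denominator suits it. At least one year of follow-up is planned, and Section 7.3 provides for obtaining local records when patients cannot travel. The outcome is secondary and descriptive, in a 38-patient pilot with no decision attached, and the most severe late events already have a one-year window in Section 11.3. The 90% half-width at a 20% rate is 1.645 × √(0.20 × 0.80 / 38) = 10.7 points, larger than any shift above. That the safety population is the denominator is an inference from Section 11.4. All of this stands and limits the weight of the point. None of it supplies the missing horizon or a rule for death and loss.

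A reader might go further and infer that late toxicity will be understated because early deaths dilute it. The documents do not support that as a general conclusion. Death is a competing event: with complete follow-up to a fixed time, events over all treated patients correctly estimate cumulative incidence in treated patients. The figure is low only relative to the risk among patients who reach month 3. Events after one year act in the opposite direction against a one-year benchmark. Row (4) equals or exceeds row (2) in every scenario run without loss. True downward bias comes from patients lost without an event and counted as event-free, and its size is unknown. The early-death percentages are also upper-end, because Section 4.1 requires a life expectancy above 3 months.

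**Conclusion.** The point holds as an undefined quantity, not as a bias of known sign. As written, the late-toxicity percentage has no horizon, an implied denominator and no treatment of death or loss, so it is not on the same basis as the one-year expectation in Section 8. In the illustration the same patients yield 14.0% at one year or 22.7% without a horizon (median 13.8 months), one on each side of 20%. If late events were confined to the first year, that upward shift would vanish and only the loss effect would remain.

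The sizes rest on constant hazards, on an assumed late risk and loss rate, and on medians from cited studies. The 7-month median runs from recurrence and describes only part of this population. The absence of a horizon and of any rule for death or loss rests on the text alone. The change is worth making before analysis, but it does not touch the primary outcome.

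**What to change.** In Sections 3.3.2 and 11.10, replace the raw percentage with the 12-month cumulative incidence of late toxicity in the safety population, timed from SBRT completion as in Section 10.2. Treat death as a competing event, censor at loss to follow-up, and give a 90% confidence interval (the Aalen-Johansen estimator serves). A Kaplan-Meier curve that censors at death should not be used, since it would overstate the cumulative incidence.

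Add as supportive: the same estimate among patients alive and in follow-up at 3 months, and the raw counts with both denominators.

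The cost is a sentence in each section, approved like any protocol change under Section 13, and slightly more analysis work. Estimates for individual conditions with few events will be imprecise. The fix leaves two things open. The Section 8 expectation covers all grade 2 or higher late gastrointestinal events, which is broader than the Section 3.2 definition. And Section 15 keeps toxicity below grade 3 off the adverse event log and case report forms although the late outcome includes grade 2 events; that is a separate and more direct route to undercounting, and it needs its own correction.
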